### **3.2.1 Rationale for choice of background therapy**

High-dose corticosteroid therapy is the mainstay of treatment for GCA; however, additional treatments that would effectively reduce the dose and duration of corticosteroid therapy are needed, thus avoiding the associated long-term toxicity and providing more durable remission of GCA. This study aims to show that secukinumab can enable patients with GCA to achieve and maintain disease control. A specific (i.e. prednisolone) taper regimen was selected for this study as a similar treatment strategy (i.e. with prednisone) proved to be effective in combination with another humanized monoclonal antibody (i.e. tocilizumab) for achieving sustained glucocorticoid-free remission in patients with GCA in the GIACTA-trial.

In this phase-3 trial, the percentage of placebo patients in remission following the 26-week taper regimen vs. 52-week taper regimen was the same (14% vs. 18%). More AEs/SAEs were recorded in the placebo groups than in the tocilizumab groups with the highest numbers in the 52-week taper regimen placebo group, which may have been the results of the effects of glucocorticoids. In the 26-week-taper regiment group, no ischemic events and in particular no cases of anterior ischemic optic neuropathy were reported. ([Stone et al 2017](#)) Due to the glucocorticoid-therapy-associated AEs and their substantial increase when it comes to long term treatment and thereby raised total glucocorticoid dose, efforts should be made to use the lowest doses of glucocorticoids for the shortest time possible when treating patients GCA ([Proven et al 2003](#)). Therefore, the 26-week corticosteroid (i.e. prednisolone) taper regimen, with a low-stringency escape strategy, was selected for this study.

In addition, a corticosteroid tapering strategy is in line with EULAR recommendations for the management of GCA ([Mukhtyar et al 2009](#), [Ponte et al 2015](#)).

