#### **4.1 Inclusion criteria**

Patients eligible for inclusion in this study must meet all of the following criteria:

1. Signed informed consent must be obtained prior to participation in the study.
2. Patient must be able to understand and communicate with the investigator and comply with the requirements of the study.
3. Male or non-pregnant, non-lactating female patients at least 50 years of age.
4. Diagnosis of GCA classified according to the following criteria:
  - Age at onset of disease  $\geq$  50 years.
  - History of ESR  $\geq$  30 mm/hr or CRP  $\geq$  10 mg/L.
  - Unequivocal cranial symptoms of GCA (new-onset localized headache, scalp or temporal artery tenderness, ischemia-related vision loss, or otherwise unexplained mouth or jaw pain upon mastication) **AND/OR** symptoms of polymyalgia rheumatica (PMR defined as shoulder and/or hip girdle pain associated with inflammatory morning stiffness).
  - Temporal artery biopsy revealing features of GCA **AND/OR** evidence of large-vessel vasculitis by angiography or cross-sectional imaging study such as magnetic resonance angiography (MRA), computed tomography angiography (CTA), positron emission tomography-computed tomography (PET-CT), or ultrasound.
5. Patients with new onset GCA or relapsing GCA:
  - Definition new onset: diagnosis of GCA within 6 weeks of Baseline Visit.
  - Definition relapsing GCA: diagnosis of GCA (in accordance with inclusion criterion no. 4)  $>$  6 weeks before Baseline Visit and in the meantime achieved remission (absence of signs and symptoms attributable to GCA and normalization of ESR ( $<$  30 mm/hr) and CRP ( $<$  10.0 mg/L) included) including previous treatment with  $\geq$  25 mg/day prednisolone equivalent for  $\geq$  2 weeks.
6. Active disease as defined by the presence of signs and symptoms of GCA (cranial or PMR) and elevated ESR  $\geq$  30 mm/hr, or CRP  $\geq$  10 mg/L, attributed to active GCA within 6 weeks of Baseline.
7. Prednisolone dose of 25-60 mg/day at Baseline.
8. Patients taking MTX ( $\leq$  25 mg/week) are allowed to continue their medication provided they have taken it for at least 3 months and are on a stable dose for at least 4 weeks prior to randomization and if they are on a stable folic acid treatment before randomization.

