### **Prednisolone**

Two different prednisolone taper regimens (Table 5-3 for patients on 40 to 60 mg/day prednisolone at Baseline; and Table 5-4 for patients on 25 to 40 mg/day prednisolone at

Baseline) will be used for both treatment arms depending on patients' prednisolone levels at Baseline. From Week 8, all patients will receive the same prednisolone level (15 mg/day) and will continue to be tapered down.

Prednisolone will be supplied by the Sponsor in an open-label fashion. Prednisolone intakes at weeks, which are not part of the assessment schedule need to be reported (date/, home administration form).

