**Table 5-3 60-40 mg/day at Baseline**

Week	Dose mg/day	Prednisolone				n/visit
		20 mg, n(tablets)	10mg, n(tablets)	5 mg, n(tablets)	1mg, n(tablets)	
0	60-40					
1	55-35					
2	50-30					
3	45-28					
4	35-25					
5	30-22					
6	25-21					
7	20		2			2
8	15		1	1		2
9	13		1		3	4
10	12		1		2	3
11	10			2		2
12	9			1	4	5
13	8			1	3	4
14	7			1	2	3
15	6			1	1	2
16	6			1	1	2
17	5			1		1
18	5			1		1
19	4				4	4
20	4				4	4
21	3				3	3
22	3				3	3
23	2				2	2
24	2				2	2
25	1				1	1
26	1				1	1
27	0					
28	0					

Grey: no site visit

**Table 5-4** 40-25 mg/day at Baseline

Week	Dose mg/day	Prednisolone				n/visit
		20 mg, n(tablets)	10mg, n(tablets)	5 mg, n(tablets)	1mg, n(tablets)	
0	40-25					
1	35-22					
2	30-21					
3	27-20					
4	25-19					
5	22-18					
6	20-17					
7	16		1	1	1	3
8	15		1	1		2
9	13		1		3	4
10	12		1		2	3
11	10			2		2
12	9			1	4	5
13	8			1	3	4
14	7			1	2	3
15	6			1	1	2
16	6			1	1	2
17	5			1		1
18	5			1		1
19	4				4	4
20	4				4	4
21	3				3	3
22	3				3	3
23	2				2	2
24	2				2	2
25	1				1	1
26	1				1	1
27	0					
28	0					

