The time to first GCA flare after remission (up to Week 52) will be summarized using Kaplan Meier curves. Patients who:

- Withdraw from the study prior to Week 52 will be censored at the time of withdrawal
- Do not have a flare up to Week 52 will be censored at Week 52

Descriptive statistics will also be provided for time to first GCA flare after clinical remission (up to Week 52).

Total cumulative prednisolone dose over 28 and 52 weeks will be summarized over time by treatment group.

The proportion of GCA patients in sustained remission at Week 52 will be analyzed using the methods outlined in Section 9.4.2. Patients who (1) do not achieve remission within 12 weeks of Baseline; or (2) are in the “escape arm”; or (3) drop out from the study prior to/on Week 52, or (4) do not have information to evaluate sustained remission response at Week 52, will be classified as non responders. Patients receiving less than the full amount of prednisolone as required by the taper, e.g. due to missing tablets, will not be classified as non-responders.

The number (and percentage) of patients on prednisolone dose  $\leq$ 5mg/day at Week 19, 28 and 52 will be summarized by treatment group.

The continuous secondary efficacy endpoints (actual value and change from baseline value) will be summarized descriptively by visit (where applicable) and by treatment group.

For SF-36, the following variables will be evaluated:

- SF-36 domain scores

- SF-36 domain score responders
  - Type I responders (improvement of  $\geq 5$  points in  $\geq 6$  domains)
  - Type II responders (improvement of  $\geq 10$  points in  $\geq 3$  domains)
- SF-36 PCS and MCS scores
- SF-36 PCS and MCS score responders
  - Type I responders (improvement of  $\geq 2.5$  points)
  - Type II responders (improvement of  $\geq 5$  points)

The EQ-5D is a questionnaire with 5 questions (regarding mobility, self-care, usual activities, pain/discomfort, and anxiety/depression) each with three categories (no problem, moderate problem, severe problems) and a health state assessment from 0 (worst possible health state) to 100 (best possible health state) (see [Section 6.5.2.1.4](#) for further details). The number and percentage of subjects in each of the three categories for each question will be presented by visit and treatment group. Summary statistics will be provided for the health state assessment by visit and treatment group.

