2.7.2 Statistical hypothesis, model, and method of analysis

The proportion of patients in sustained remission until Week 52 (Yes, No) will be summarized descriptively for each treatment group. Note: Sustained remission at Week 52 refers to patients without flare until Week 52 and in adherence to the protocol prednisolone taper regimen. Flare is determined by the investigator and defined as the recurrence after remission of signs or symptoms of GCA and/or ESR \geq 30 mm/hr and/or CRP \geq 10 mg/L attributable to GCA. In addition, the reasons why a patient is determined to be a responder or non-responder to patients in sustained remission until Week 52 will be summarized.

The proportion of patients in remission (Yes, No) at each time point will be summarized descriptively for each treatment group. Note: Remission refers to the absence of flare. This summary table will only summarize remission information up to 4 weeks post last administration of study treatment.

The time to first GCA flare after remission (up to and including Week 52) will be summarized using Kaplan Meier curves. Descriptive statistics will also be provided for time to first GCA flare after remission in days (up to and including Week 52). This will also include information on follow-up. Follow-up is defined as:

• (Date of event or censoring – Baseline date) + 1 (regardless of censoring)

Total cumulative prednisolone dose from the first dose of co-administered prednisolone treatment to Weeks 26, Week 28, and 52 will be summarized over time by treatment group. Note: Prednisolone dose refers to prednisolone dose taken for GCA.

The number and percentage of patients on prednisolone dose \leq 5mg/day at Week 19, 28 and 52 will be summarized by treatment group. Note:

- Prednisolone dose refers to prednisolone dose taken for GCA.
- Prednisolone dose refers to the average co-administered prednisolone treatment in the week of interest.

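### Cumulative prednisolone is summarised by arm with no account of starting dose, which adds avoidable chance noise to a descriptive secondary endpoint

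*SAP*

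**What the plan says.** Cumulative corticosteroid dose to Weeks 28 and 52 is a listed secondary efficacy measure (Protocol Table 2-1, SAP Table 1-1). The motive is in Protocol 3.2.1: "additional treatments that would effectively reduce the dose and duration of corticosteroid therapy are needed".

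The two documents plan the same kind of analysis.

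- Protocol 9.5.1: "Total cumulative prednisolone dose over 28 and 52 weeks will be summarized over time by treatment group".
- SAP 2.7.2: "Total cumulative prednisolone dose from the first dose of co-administered prednisolone treatment to Weeks 26, Week 28, and 52 will be summarized over time", again by treatment group.

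Neither adjusts for starting dose, splits the summary by taper table or sets the total against the scheduled amount. Baseline-dose subgroups exist, but Protocol 9.4.5 and SAP 2.5.4 attach them to the primary endpoint. The only subgroups named in SAP 2.7.2 are for CRP and ESR.

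Entry requires "Prednisolone dose of 25-60 mg/day at Baseline". Protocol 5.5.4 then provides two schedules, Table 5-3 for 40-60 mg/day and Table 5-4 for 25-40 mg/day, which later merge: "From Week 8, all patients will receive the same prednisolone level (15 mg/day) and will continue to be tapered down". Protocol 5.3 states the allocation ratio and mentions no stratification factor.

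**The concern.** Part of each patient's total is fixed at entry. The starting dose, reached during screening at the investigator's discretion, sets the schedule through Week 7, and study drug cannot change that scheduled part. A treatment effect shows mainly through escape or extra prednisolone, and to a small extent through the missed tablets that the protocol tolerates. The raw total adds these departures to a scheduled amount that varies between patients for reasons unrelated to the randomised treatment.

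With about 25 patients per arm and no described stratification, a chance difference in starting dose passes straight into the arm difference in cumulative dose, in either direction, and widens the spread. The SAP introduction says the results are to support a phase III programme, so a descriptive difference in 50 patients is likely to be read as evidence on steroid sparing.

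**Working it through.** The documents state no cumulative total, SD or power for this endpoint, so there is no figure of the plan's own to reproduce.

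**Scheduled totals.** Inputs are the daily doses in Protocol Tables 5-3 and 5-4, in weekly steps of 7 days, Weeks 0 to 26. The schedule is 0 mg from Week 27, so the totals to Weeks 28 and 52 are equal.

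- 60 mg start, Weeks 0-7: 60+55+50+45+35+30+25+20 = 320
- 40 mg start, Table 5-3: 40+35+30+28+25+22+21+20 = 221
- 40 mg start, Table 5-4: 40+35+30+27+25+22+20+16 = 215
- 25 mg start: 25+22+21+20+19+18+17+16 = 158
- Common part, Weeks 8-26: 15+13+12+10+9+8+7+6+6+5+5+4+4+3+3+2+2+1+1 = 116

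Total = 7 x (Weeks 0-7 sum + 116):

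- 60 mg: 7 x 436 = 3,052 mg
- 40 mg, Table 5-3: 7 x 337 = 2,359 mg
- 40 mg, Table 5-4: 7 x 331 = 2,317 mg
- 25 mg: 7 x 274 = 1,918 mg

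The range is 3,052 - 1,918 = 1,134 mg, or 1,134/1,918 = 59%. At exactly 40 mg/day the two tables differ by 42 mg.

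**Noise between arms.** SE of the arm difference = SD x sqrt(2/25). The starting-dose distributions are assumptions, as is linear interpolation between the printed ends of each range.

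| Assumed starting doses | SD (mg) | SE (mg) | 95% chance range (mg) |
|---|---|---|---|
| Uniform 30-50 | 196 | 55 | ±108 |
| Uniform 25-60 | 337 | 95 | ±187 |
| 25/30/40/50/60, equal weights | 418 | 118 | ±232 |
| Half at 25, half at 60 | 567 | 160 | ±314 |

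Under the uniform 25-60 mg case, simulation puts the chance that the arms' mean scheduled doses differ by more than 100 mg at about 29%, and by more than 200 mg at about 3%.

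**Scale against a possible effect.** Suppose, as an assumption, that each non-responder takes E mg extra on average with a coefficient of variation of 0.5, and that response is 56% versus 18% (the rates expected in SAP 2.5.2). The arm difference is 0.38 x E. Within an arm with response rate p, the variance of the extra dose is 1.25 x E² x (1-p) - (E x (1-p))², averaged over the two arms. With uniform 25-60 mg starts:

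- E = 500: difference 190 mg; SE 127 mg raw, 84 mg with the scheduled part removed
- E = 1,000: difference 380 mg; SE 193 mg raw, 168 mg removed
- E = 2,000: difference 760 mg; SE 350 mg raw, 337 mg removed

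The gain is large if escape dosing is modest and small if it is heavy.

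**Is a linear covariate enough?** A straight line from (25, 1,918) to (60, 3,052) has slope 1,134/35 = 32.4 mg per mg/day. At 40 mg it gives 1,918 + 15 x 32.4 = 2,404 mg, against 2,359 or 2,317 mg from the tables. Under the same interpolation the largest departure is 87 mg, at 40 mg/day, out of a range of 1,134 mg. A linear term removes most of the scheduled variation.

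**The case against.** Several points on the other side stand.

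- **Randomisation.** It balances starting dose in expectation. A reader might infer from the 1,134 mg gap that the arm comparison is confounded. The documents do not support that: the figure compares two patients at opposite ends of the entry range, and between arms only chance imbalance remains.
- **Descriptive status.** There is no test, threshold or error rate here, and the go criteria in SAP 2.5.2 use only the primary endpoint's risk difference.
- **Existing tables.** SAP 2.4.1 gives mean daily dose by arm for each taper week, SAP 2.3.2 tabulates baseline dose as at least 40 versus below 40 mg/day, and the endpoint of 5 mg/day or less at Weeks 19, 28 and 52 does not depend on the starting schedule. Nothing is scheduled after Week 26, so the increment from Week 26 to Week 52 is wholly above schedule.

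These tables reveal an imbalance or sidestep it, but they do not correct the cumulative comparison. The weekly means use the Safety Set, whereas this endpoint uses the FAS. Within the upper baseline category, scheduled totals still span 3,052 - 2,359 = 693 mg.

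A further tempting step is to treat each patient's schedule as known exactly and make dose above schedule the basis of the steroid-sparing conclusion. The documents do not support this either. For Weeks 0-6 the tables print only ranges, and at 40 mg/day both apply. The protocol defines the endpoint as total exposure, which a dose-above-schedule measure would displace. Subtracting a full schedule from a patient who leaves early would also look like sparing.

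**Conclusion.** The point holds as a minor one. The plan leaves a known baseline determinant of cumulative prednisolone out of the arm comparison. The scheduled totals follow exactly from the printed ends of the two tables. The arm-level figure, an SE of about 95 mg with a range of about 55 to 160 mg, rests on assumed starting-dose distributions, 25 patients per arm and interpolation within the tables. The absence of stratification is inferred from the protocol's silence. The consequence is lost precision and possible chance imbalance in a descriptive secondary summary. The primary analysis and the go decision are unaffected.

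**What to change.** In SAP 2.7.2, keep the raw total by arm as the protocol-defined endpoint. Add a supportive arm difference in cumulative dose to Weeks 28 and 52, with an interval, from a linear model with treatment and baseline prednisolone dose as a continuous covariate. Escape dosing is likely to skew the totals, so a robust or bootstrap interval would be sensible.

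Two optional displays:

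- Signed recorded-minus-scheduled dose, counting the schedule only over each patient's observed follow-up so that early withdrawal does not pass for sparing.
- Cumulative dose from Week 8 (study day 57) onward, labelled as a check that misses earlier escapes.

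Before any recorded-minus-scheduled variable is derived, the Protocol 5.5.4 text and Tables 5-3 and 5-4 must be reconciled on two matters: the dose ranges printed for Weeks 0-6, and the two tables that apply at 40 mg/day. The adherence rule in SAP 2.5.1 also refers to a stated dosage, so it needs the same clarification. The adjusted difference itself does not need it.

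The cost is one extra model and table from data already collected, with no change to trial conduct. It should be specified before unmasking.

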## 5.6 Study completion and discontinuation

### 5.6.1 Study completion and post-study treatment

A subject will be considered to have completed the study when the subject has completed the last visit planned in the protocol. (i.e. 52-week treatment period, and 8-week follow-up period). As per the study design, patients who do not achieve remission by Week 12, experience a flare after remission or cannot adhere to the prednisolone taper regimen will enter “escape”. Upon entering “escape”, patients will receive prednisolone at a dose determined by the Investigator’s clinical judgment and continue to receive secukinumab or placebo in a blinded manner until Week 48. No further secukinumab treatment will be provided after Week 48. No further prednisolone treatment will be provided after Week 52.

Study completion is defined as when the last patient completes their End of Study Visit, and any repeat assessments associated with this visit have been documented and followed-up appropriately by the Investigator, or in the event of an early study termination decision, the date of that decision.

Normally, all randomized and/or treated patients should have a safety follow-up call conducted 60 days after last administration of study treatment; however, the 60 days falls within the study 8-week follow-up period, where no s.c. study treatment is given; therefore, the safety follow-up is part of the End of Study. As so far, no indication for an increased incidence or progression of malignancies was observed in clinical studies of secukinumab, no further monitoring after the two follow-up visits is required.

All SAEs reported during this time period must be reported as described in [Section 7.1.3](#).

After study participation, the patients will continue to be treated at the investigators discretion according to local practice. The investigator must provide follow-up medical care for all patients who prematurely withdraw from the study, or must refer them for appropriate ongoing care.

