## **6 Visit schedule and assessments**

Table 6-1 lists all of the assessments and indicates with an "x" when the visits are performed.

Assessment schedule lists all of the assessments when they are performed. All data obtained from these assessments must be supported in the patient's source documentation.

- All questionnaires will be completed prior to the subject seeing the investigator for any clinical assessment or evaluation.

- All efficacy assessments should be performed prior to administration of study treatment.

Patients should be seen for all visits/assessments as outlined in the assessment schedule or as close to the designated day/time as possible. Missed or rescheduled visits should not lead to automatic discontinuation.

Patients who prematurely discontinue the study treatment (s.c. secukinumab or placebo) are encouraged to remain in the study to continue the study-related assessments until completion of the study.

Patients who prematurely discontinue completely from the study for any reason should return for the End of Treatment visit (EOT) to conduct the Week 52 assessments (4 weeks after the last study treatment administration of secukinumab), as well as return for the follow-up visits (Week 56 and Week 60).

At the End of Treatment visit, all dispensed prednisolone should be reconciled, and the AE and concomitant medications recorded on the eCRF.

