2.1.1.12 Visit windowing

The study day for each visit will be derived; this day will then be used to determine the analysis visit based on the visit windows outlined in Table 2-1. In addition the study day associated with each week will also be derived as a supportive analysis (see Table 2-2).

If more than one analysis visit occurs at a visit, only one will be selected for summary tables but all visits will be listed.

For categorical variables, the closest to the target study day is chosen (if two assessments have the same distance, than the earlier one will be chosen).

For continuous variables, the worst record is selected. It is noted that in the analyses performed, worst case is always well defined (e.g., for urine protein values "+" and "++", the worst case is defined as "++").

The analysis visit will be used for listing of visit and period. If a visit falls after the last visit window (i.e. after Day 435) it is not assigned an analysis visit and will be listed under the label "After last scheduled visit" (i.e. "After Week 60").

Table 2-1 Visit windows

Timepoint	Analysis visit	Target Study day	Visit window
	•		(study days)
	Baseline	1	-42 to 1
4	Week 1	8	2 to 11
5	Week 2	15	12 to 18
6	Week 3	22	19 to 25
7	Week 4	29	26 to 43
8	Week 8	57	44 to 71
9	Week 12	85	72 to 99
10	Week 16	113	100 to 127
11	Week 20	141	128 to 155
12	Week 24	169	156 to 183
13	Week 28	197	184 to 211
14	Week 32	225	212 to 239
15	Week 36	253	240 to 267
16	Week 40	281	268 to 295
17	Week 44	309	296 to 323
18	Week 48	337	324 to 351
19	Week 52	365	352 to 379
20	Week 56	393	380 to 407
21	Week 60	421	408 to 435

Table 2-2 Weekly period for co-administered prednisolone treatment

Timepoint	Week	Week definition
3	Week 0	Study day 1 to Study day 7
4	Week 1	Study day 8 to Study day 14
5	Week 2	Study day 15 to Study day 21
6	Week 3	Study day 22 to Study day 28
7	Week 4	Study day 29 to Study day 35
8	Week 5	Study day 36 to Study day 42
9	Week 6	Study day 43 to Study day 49
10	Week 7	Study day 50 to Study day 56
11	Week 8	Study day 57 to Study day 63
12	Week 9	Study day 64 to Study day 70
13	Week 10	Study day 71 to Study day 77
14	Week 11	Study day 78 to Study day 84
15	Week 12	Study day 85 to Study day 91
16	Week 13	Study day 92 to Study day 98
17	Week 14	Study day 99 to Study day 105

Timepoint	Week	Week definition
18	Week 15	Study day 106 to Study day 112
19	Week 16	Study day 113 to Study day 119
20	Week 17	Study day 120 to Study day 126
21	Week 18	Study day 127 to Study day 133

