22	Week 19	Study day 134 to Study day 140
23	Week 20	Study day 141 to Study day 147
24	Week 21	Study day 148 to Study day 154
25	Week 22	Study day 155 to Study day 161
26	Week 23	Study day 162 to Study day 168
27	Week 24	Study day 169 to Study day 175
28	Week 25	Study day 176 to Study day 182
29	Week 26	Study day 183 to Study day 189
30	Week 27	Study day 190 to Study day 196
31	Week 28	Study day 197 to Study day 203
32	Week 29	Study day 204 to Study day 210
33	Week 30	Study day 211 to Study day 217
34	Week 31	Study day 218 to Study day 224
35	Week 32	Study day 225 to Study day 231
36	Week 33	Study day 232 to Study day 238
37	Week 34	Study day 239 to Study day 245
38	Week 35	Study day 246 to Study day 252
39	Week 36	Study day 253 to Study day 259
40	Week 37	Study day 260 to Study day 266
41	Week 38	Study day 267 to Study day 273
42	Week 39	Study day 274 to Study day 280
43	Week 40	Study day 281 to Study day 287
44	Week 41	Study day 288 to Study day 294
45	Week 42	Study day 295 to Study day 301
46	Week 43	Study day 302 to Study day 308
47	Week 44	Study day 309 to Study day 315
48	Week 45	Study day 316 to Study day 322
49	Week 46	Study day 323 to Study day 329
50	Week 47	Study day 330 to Study day 336
51	Week 48	Study day 337 to Study day 343
52	Week 49	Study day 344 to Study day 350
53	Week 50	Study day 351 to Study day 357
54	Week 51	Study day 358 to Study day 364
55	Week 52	Study day 365 to Study day 371
56	Week 53	Study day 372 to Study day 379
57	Week 54	Study day 380 to Study day 386
58	Week 55	Study day 387 to Study day 393
59	Week 56	Study day 394 to Study day 400

Page 17 of 53

Timepoint	Week	Week definition
60	Week 57	Study day 401 to Study day 407
61	Week 58	Study day 408 to Study day 414
62	Week 59	Study day 415 to Study day 421
63	Week 60	Study day 422 to Study day 429

Note: Co-administered treatment refers to prednisolone taken for GCA. There should be a 26-week prednisolone taper regimen however a patient may take additional prednisolone over the 52-week treatment period.

2.2 **Analysis sets**

The following analysis sets will be used for the patients of interest:

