2.7.1 Secondary endpoints

The following secondary endpoints will be analyzed:

- Proportion of GCA patients who adhere to the prednisolone taper regimen and are in sustained remission at Week 52
- Remission rate at Week 12
- Time to first GCA flare after Baseline (up to and including Week 52)
- Total cumulative prednisolone dose from start of co-administered treatment to Week 28, 52
- Proportion of patients on prednisolone dose ≤ 5 mg/day at Week 19, 28, 52
- Change from Baseline in PhGA VAS at Week 4, 8, 12, 16, 20, 24, 28, 36, 44 and 52
- Change from Baseline in PGA VAS at Week 4, 8, 12, 16, 20, 24, 28, 36, 44 and 52
- Change from Baseline in FACIT-Fatigue at Week 4, 8, 12, 16, 20, 24, 28, 36, 44 and 52
- Change from Baseline in SF-36 at Week 4, 8, 12, 16, 20, 24, 28, 36, 44 and 52
- Change from Baseline in EQ-5D at Week 4, 8, 12, 16, 20, 24, 28, 36, 44 and 52
- Change from Baseline in CRP (mg/L) at Week 4, 8, 12, 16, 20, 24, 28, 36, 40, 44, 48, 52
- Change from Baseline in ESR (mm/hr) at Week 4, 8, 12, 16, 20, 24, 28, 36, 40, 44, 48, 52

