- Prednisolone dose for GCA will be based on the information collected on the "Dosage Administration Record-Prednisolone" eCRF. However as the prednisolone taper regimen is planned to be 26-weeks in duration, the Investigator is not required to enter daily prednisolone records on the "Dosage Administration Record-Prednisolone" eCRF post Week 26 unless the patient has taken additional prednisolone for GCA. Therefore if the patient is still in the study at the post Week 26 week of interest and has no prednisolone information in the "Dosage Administration Record-Prednisolone" eCRF for that week of interest the patient will be regarded as having 0 mg/day at that week of interest.

Descriptive summary statistics for the change as well as relative change from baseline of PhGA VAS to each study visit of interest will be presented for each treatment group. Change from baseline will only be summarized for patients with both baseline and post baseline values.

The analysis of the PRO secondary endpoints is detailed in Section 2.10.

Descriptive summary statistics for the change from baseline of CRP and ESR to each study visit of interest will be presented for each treatment group. Change from baseline will only be summarized for patients with both baseline and post baseline values. Further details are provided in Section 2.8.3. This analysis will also be presented for the following subgroups:

- Sustained remission until Week 28 (Yes, No)
- Sustained remission until Week 52 (Yes, No)

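### The Week 52 prednisolone endpoint is scored on Days 365-371, mostly after an on-time End of Treatment visit, and a blank week is set to 0 mg/day without checking other records

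*SAP*

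**What the plan says.** The endpoint in SAP 2.7.1 is "Proportion of patients on prednisolone dose ≤ 5 mg/day at Week 19, 28, 52". SAP 2.7.2 summarises it as a number and percentage by arm, with no test. It adds that "Prednisolone dose refers to the average co-administered prednisolone treatment in the week of interest" and takes the dose from the prednisolone dosing form.

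SAP Table 2-2, headed "Weekly period for co-administered prednisolone treatment", gives Week 52 as "Study day 365 to Study day 371". SAP 2.7.2 does not cite this table, but it is the only definition of prednisolone weeks in the SAP, and SAP 2.4.1 uses it for weekly average doses. The note under it says "however a patient may take additional prednisolone over the 52-week treatment period". SAP Table 2-1 gives the Week 52 visit, which the protocol's assessment schedule labels EOT, a target of Day 365 and a window of Days 352-379.

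On supply, Protocol 5.6.1 states: "No further prednisolone treatment will be provided after Week 52". Protocol 6 states: "At the End of Treatment visit, all dispensed prednisolone should be reconciled". Patients then stay in the study for follow-up visits at Weeks 56 and 60.

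On missing records, SAP 2.7.2 says that after Week 26 daily entries are needed only if the patient has taken additional prednisolone for GCA. If a patient still in the study has no entry, "for that week of interest the patient will be regarded as having 0 mg/day at that week of interest".

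**The concern.** The endpoint is meant to show whether patients are off, or nearly off, prednisolone at the end of the treatment period. The scored week instead begins on the day that period nominally closes. This is where dosing-form data are most likely to thin out: study tablets have been reconciled, supply has ended, and any further prednisolone comes through local care. A blank week at that point need not mean that no drug was taken, yet the zero rule reads it that way.

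The patients exposed to this are those still on prednisolone at the end of treatment, chiefly those in escape. An error from the zero rule runs one way only: a patient above 5 mg/day is counted as a success, and never the reverse. The problem is particular to Week 52. At Week 19 the zero rule does not apply, and at Week 28 study supply and treatment visits continue.

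**Working it through.** **1. Reproduce the SAP's week.** Table 2-2 follows week w = Days 7w + 1 to 7w + 7 up to this point. For w = 52: 7 × 52 + 1 = 365 and 7 × 52 + 7 = 371, which matches the stated Days 365-371. Week 19 (Days 134-140) and Week 28 (Days 197-203) also match.

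**2. Place it against the end of treatment.**
- The 52-week treatment period is 52 × 7 = 364 days, so all seven scored days lie beyond Day 364.
- With the EOT visit on its target, Day 365, the days after the visit are 366-371: six of seven.
- SAP 2.7.2 limits its remission summary to 4 weeks after the last study dose. For a Week 48 dose on target this is Day 337 + 28 = Day 365. The prednisolone week runs six days past that cutoff.

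**3. Vary the EOT day over the 28 days of the window (352-379).** Assumption, not in the documents: dosing-form entries stop at the EOT visit.

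| Entries run through | Week wholly blank (scored 0) | Partly recorded | Fully recorded |
|---|---|---|---|
| the visit day | visits on Days 352-364: 13 | Days 365-370: 6 | Days 371-379: 9 |
| the day before | visits on Days 352-365: 14 | Days 366-371: 6 | Days 372-379: 8 |

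These count possible visit days; they are not probabilities. Visits on Days 372-379 are unaffected, because the whole scored week precedes them.

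**4. The divisor.** If only Day 365 is recorded, at dose D, the zero rule does not apply. The weekly average is then D if divided by recorded days, or D/7 if divided by seven. The SAP does not say which. Under D/7 the condition D/7 ≤ 5 is met for any D up to 35 mg: 10 mg gives 1.43 mg/day, 35 mg gives 5.00 and 40 mg gives 5.71. Under the other reading, D itself is compared with 5 mg.

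**5. Weight of one patient.** SAP 1.1 plans at least 25 per arm. One misclassified patient moves that arm's rate by 1/25 = 4 percentage points. For an assumed 1 to 5 such patients in an arm, the shift is 4 to 20 points.

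**The case against.** The strongest reply is that recording does not stop at EOT. SAP 2.7.2 requires entries after Week 26 whenever additional prednisolone for GCA is taken and sets no end date. Protocol 5.5.4 requires all dose changes during the study to be recorded on the eCRF. Table 2-2 runs to Week 60, and the SAP counts prednisolone taken for GCA without limiting it to sponsor tablets. Tablet reconciliation is drug accountability, not closure of a form. On this reading a zero is assigned only where a blank is correct.

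That stands as far as it goes. A reader might infer that the zero rule by itself gives a wrong value for escape patients, or that nothing requires their later prednisolone to be recorded. The documents do not support either: misclassification needs an entry that was missed or made elsewhere. That remains a real possibility, since Protocol 5.5.7 sends other medication to whichever eCRF page is appropriate, and the zero rule consults only the dosing form. Nor does the reply meet the timing point. Even with complete records, an on-time visit leaves six of the seven scored days after EOT.

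A reader might also infer a definite shrinkage of the difference between arms. That would need the number above 5 mg/day and the share with blank weeks in each arm, and the documents give neither.

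The stakes are limited too. The endpoint is descriptive, there is no key secondary objective, the criteria for proceeding use the Week 28 primary endpoint, and Week 52 sustained remission already counts escape patients as non-responders.

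**Conclusion.** The point holds as a misplaced scoring week combined with an unchecked zero rule. That Week 52 is Days 365-371 and starts on the target EOT day follows from the SAP's own tables, taking Table 2-2 as the definition SAP 2.7.2 intends. For an on-time visit the endpoint mostly measures prednisolone after the treatment period.

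Misclassification is conditional: it requires prednisolone taken after EOT to be missing from the dosing form, and it does not arise for EOT visits on Days 372-379. Its size cannot be derived from the documents beyond 4 points per patient at 25 per arm. Where the zero rule does misclassify, it turns a failure into a success. The undefined divisor is a separate gap that matters when the week is partly recorded. The change is worth making because it is cheap and puts the measurement back inside the treatment period.

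**What to change.** In SAP 2.7.2:

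1. Score Week 52 on the seven days ending the day before the actual Week 52/EOT visit. The Week 51 row of Table 2-2 (Days 358-364) is a simpler alternative, but it still falls wholly after EOT visits on Days 352-357.
2. State the divisor for the weekly average and how a partly recorded week is handled.
3. Before setting a blank week to 0 mg/day, check the preceding dosing records, escape status and concomitant-medication records. Do not set 0 where these show ongoing prednisolone for GCA.

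Do not carry the last recorded dose forward for every escape patient. One who escaped, later stopped prednisolone and correctly has no further entries could be given an old non-zero dose, and a true success would become a failure.

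The cost is SAP wording, minor programming and a small departure from the Table 2-2 grid. No new data are needed.
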